10.4.4.5 Clinical Institute Withdrawal Assessment-Benzodiazepines (CIWA-B)

Subjects not entering the open label extension study (OLE) are tapered off study medication after completing the Maintenance Period (or if discontinued from the study). As part of monitoring of subjects for withdrawal symptoms during the Taper Period, the CIWA-B evaluation is performed at the end of the Maintenance Period (Visit7), at the end of the Taper Period (Visit 8), and at the Safety follow-up visit (Visit 9). The CIWA-B questionnaire contains 22 questions, which are utilized to determine the type and the severity of withdrawal symptoms, ranging from mild, moderate, severe and very severe withdrawal symptoms (Busto et al, 1989). Subscores of each of the first 20 questions (scores from 0-4) are summed up to a total score:

Total score	Interpretation
-------------	----------------

1-20	Mild withdrawal
21-40	Moderate withdrawal
41-60	Severe withdrawal
61-80	Very severe withdrawal

In case of a missing sub score the total score is set to missing. The remaining two items of the 22 ask for sleeping duration and time to fall asleep. A by-subject listing will be provided, presenting the response values to all assessment parameters as well as the CIWA-B scores. In addition, a descriptive summary table will be prepared for total CIWA-B scores at scheduled visits.

11 OTHER ANALYSIS

Analyses for the exploratory nonhereditary pharmacogenomics and pharmacogenetics variables will be described in separate documents.

12 COVID-19 IMPACT

The impact of COVID-19 global pandemic on this study is detailed in section 3.10. COVID-19 impact will be summarized by impact category and impacted visit. The data including visit, date, relationship to COVID-19, impact category and narrative of event will be listed for the RS, if the subject has been impacted.

14 APPENDICES

14.1 PCST Criteria for Hematology, Serum Chemistry and Urinalysis Parameters

14.1.1 Hematology

PARAMETER	AGE RANGE	UNIT (conventional)	ABNORMALITY CRITERIA (conventional)	UNIT (standard)	ABNORMALITY CRITERIA (standard)
Hematocrit	<2y	%	≤27 >45	%	≤27 >45
	2y - <18y		≤29 >47		≤29 >47
	≥18y		≤85% of LLN ≥115% of ULN)		≤85% of LLN ≥115% of ULN
Hemoglobin	<2y	g/dL	≤9.0 >15.0	g/L	≤90 >150
	2y - <18y		≤9.5 >16.0		≤95 >160
	≥18y		≤85% of LLN ≥115% of ULN		≤85% of LLN ≥115% of ULN
WBC/Leukocytes	<12y	10 ⁹ /L	≤3.5 >15.0	G/L	≤3.5 >15.0
	≥12y		≤3.0 >12.0		≤3.0 >12.0
Neutrophils Absolute	>1m	10 ⁹ /L	<1.5	G/L	<1.5
Lymphocytes	<6m	%	≤30.0	%	≤30.0
	6m - <6y		≤22.0		≤22.0
	6y - <18y		≤12.0 ≥80.0		≤12.0 ≥80.0
	≥18y		≤10.0 ≥80.0		≤10.0 ≥80.0
Basophils	>1m	%	≥3.0	%	≥3.0
Eosinophils	>1m	%	≥10.0	%	≥10.0
Monocytes	>1m	%	≥20.0	%	≥20.0
Platelets	>1m	10 ⁹ /L	≤100 >600	G/L	≤100 >600
RBC/ Erythrocytes	<2y	10 ¹² /L	<3.0	T/L	<3.0

PARAMETER	AGE RANGE	UNIT (conventional)	ABNORMALITY CRITERIA (conventional)	UNIT (standard)	ABNORMALITY CRITERIA (standard)
	≥2y		<3.5		<3.5

Abbreviations: F=female; M=male; m=month; y= year. A month is defined as 30 days; a year is defined as 365.25 days.

This document cannot be used to support any marketing authorization application and any extensions or variations thereof.

REDACTED COPY

14.1.2 Serum Chemistry

PARAMETER	AGE RANGE	UNIT (conventional)	ABNORMALITY CRITERIA (conventional)	UNIT (standard)	ABNORMALITY CRITERIA (standard)
AST (SGOT)	<14y	U/L	>180	U/L	>180
	≥14y		>144		>144
ALT (SGPT)	1y - <18y	U/L	>90	U/L	>90
	≥18y		>123		>123
Alkaline Phosphatase	<4y	U/L	>690	U/L	>690
	4y - <10y		>834		>834
	10y - <18y		>1174		>1174
	≥18y		>432 (F) >933 (M)		>432 (F) >933 (M)
GGT	<6m	U/L	>522	U/L	>522
	6m - <1y		>279		>279
	1y - <13y		>66		>66
	13y - <18y		>126		>126
	≥18y		>255		>255
Total Bilirubin	>1m	mg/dL	≥1.5	umol/L	≥25.656
Total Protein	2m - <1y	g/dL	<3.0 >10.0	g/L	<30 >100
	≥1y		<4.3 >10.0		<43 >100
Albumin	<1y	g/dL	<1.6 >6.0	g/L	<16 >60
	≥1y		<2.4 >7.0		<24 >70
BUN	<1y	mg/dL	>21	mmol/L	>7.497
	≥1y		>30		>10.71
Urea	<1y	mg/dL	>42	mmol/L	>7.014

PARAMETER	AGE RANGE	UNIT (conventional)	ABNORMALITY CRITERIA (conventional)	UNIT (standard)	ABNORMALITY CRITERIA (standard)
	≥1y		>60		>10.02
Creatinine	1y - <10y	mg/dL	>0.9	umol/L	>79.56
	10y - <16y		>1.4		>123.76
	≥16y		>1.6		>141.44
Creatinine Clearance*	All	mL/min	<70	mL/s	<1.169
Calcium	<1y	mg/dL	<6.9 >12.2	mmol/L	<1.725 >3.05
	1y - <18y		<7.4 >11.7		<1.85 >2.925
	≥18y		<7.9 >11.1		≤1.975 >2.775
Phosphorous	<1y	mg/dL	<1.8 >8.2	mmol/L	<0.5814 >2.6486
	≥1y		<1.8 >7.4		<0.5814 >2.3902
Potassium	<1y	mEq/L	<3.0 >6.5	mmol/L	<3.0 >6.5
	≥1y		<3.0 >5.8		<3.0 >5.8
Sodium	>1m	mEq/L	≤130 ≥150	mmol/L	≤130 ≥150
Glucose	>1m	mg/dL	<50 >180	mmol/L	<2.775 >9.99
Total Cholesterol	1y - <18y	mg/dL	>250	mmol/L	>6.475
	≥18y		>300		>7.77
LDL (calculated)	1y - <18y	mg/dL	>140	mmol/L	>3.626
	≥18y		>200		>5.18
HDL	≤2y	mg/dL	<10	mmol/L	<0.259
	>2y		<20		<0.518
Triglycerides	<1y	mg/dL	>750	mmol/L	>8.475
	≥1y		>250		>2.825

PARAMETER	AGE RANGE	UNIT (conventional)	ABNORMALITY CRITERIA (conventional)	UNIT (standard)	ABNORMALITY CRITERIA (standard)
Uric Acid	<1y	mg/dL	>7.7	umol/L	>457.996
	1y - <13y		>6.5		>386.62
	13y - <18y		>8.6		>511.528
	≥18y		>6.8 (F) >9.6 (M)		>404.464 (F) >571.008 (M)
Thyroxine (T4)	<1y	ug/dL	≤4.3 ≥18.4	nmol/L	≤55.3453 ≥236.8264
	≥1y		≤3.8 ≥13.5		≤48.9098 ≥173.7585
Globulin	<1y	g/dL	<1.0 >3.8	g/L	<10 >38
	≥1y		<1.2 >4.4		<12 >44

Abbreviations: ALT= alanine aminotransferase; AST = aspartate aminotransferase; BUN = blood urea nitrogen; dL = deciliter; F=female; GGT: gamma-glutamyltransferase; HDL = high density lipoprotein; LDL = low density lipoprotein; L = liter; M=male; m = month (a month is defined as 30 days) mg = milligram; mmol = millimoles; µg = microgram; U = unit; ULN = upper limit of normal; y = years (a year is defined as 365.25 days)

*Schwartz equation (patients <12y): $Cr\ Cl\ ml/min = [Height\ (cm) * 0.55] / \text{serum creatinine}$
Cockcroft equation (patients ≥12y): Male: $Cr\ Cl\ ml/min = [(140-age) * \text{body weight (kg)}] / (72 * \text{serum creatinine})$; Female: $Cr\ Cl\ ml/min = [(140-age) * \text{body weight (kg)}] / (72 * \text{serum creatinine}) * 0.85$

14.1.3 Urinalysis

Qualitative urine parameters are generally reported by a descriptive score, which differs among laboratories. For data analysis purpose, a four-point scale is used. Five-point, six- point, or seven-point scales will be collapsed into a four-point scale first. A value is considered possibly clinically significant treatment emergent abnormal if an upward shift of at least 2 degrees from the baseline occurs under investigational treatment. To collapse the results in a five-point scale into a four-point scale, the lowest two positive results will be combined (see example below). For results reported with a scale of more than five-point, please consult your study physician for how to collapse into four-point scale.

Original Five-point Scale	Four-point Scale
Negative/None	Negative/None
Trace/Rare/Mild/A Few	Trace/1+/Rare/Mild/A Few
1+	
2+/Mod	2+/Mod
3+/Sev	3+/Sev

This document cannot be used to support any marketing authorization application and any extensions or variations thereof.

14.2 Abnormal Criteria for Vital Sign and Body Weight Parameters

Abnormality criteria to be applied in the assessment of vital signs parameter values are given below.

PARAMETER	AGE RANGE	ABNORMALITY CRITERIA
Pulse Rate (beats/minute)	<6m	<100
	6m - <3y	<90
	3y - <12y	<60
	12y - <17y	<50
	≥17y	<50 and a decrease from Baseline of ≥15
Systolic Blood Pressure (mmHg)	<6m	<60
	6m - <3y	<70
	3y - <12y	<80
	12y - <17y	<90
	≥17y	<90 and a decrease from Baseline of ≥20
Diastolic Blood Pressure (mmHg)	<6m	<40
	6m - <3y	<45
	3y - <12y	<50
	12y - <17y	<50
	≥17y	<50 and a decrease from Baseline of ≥15
Respiratory Rate (breaths/minute)	<6m	<25
	6m - <3y	<20
	3y - <12y	<15
	≥12y	<10

PARAMETER	AGE RANGE	ABNORMALITY CRITERIA
Temperature	>1m	>101 °F (38.3°C)
Body Weight	1m - <17y	<3% or >97% of the normal body weight growth curve ranges based on gender and the age of subject on date of weight assessment ^a
	≥17y	≥ 10% change from Baseline (an increase or a decrease) ^a

Abbreviations: m = month, y = year. A month is defined as 30 days; a year is defined as 365.25 days. ^a source: <http://www.cdc.gov/growthcharts/>

This document cannot be used to support any marketing authorization application and any extensions or variations thereof.

REDACTED COPY

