#### **General**

1. An Institutional Review Board (IRB)/Independent Ethics Committee (IEC) approved written ICF is signed and dated by the subject or by the parent(s) or legal representative, where applicable. The ICF or a specific Assent form, where required, will be signed and dated according to country-specific regulations.
2. Subject/legal representative is considered reliable and capable of adhering to the protocol (eg, able to understand and complete diaries), visit schedule, and medication intake according to the judgment of the Investigator.
3. Subject is an adult (18 years of age or more).
4. Subject is of normal weight of at least 40kg (for males and females).

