### **11.7.1 Vital signs measurement**

Vital signs will be measured at the scheduled time points presented in [Table 5-1](#).

Vital signs including pulse rate, respiratory rate, SBP, and DBP will be measured in supine position, after 5 minutes of rest. Any clinically significant abnormality in the view of the Investigator will be recorded as an AE.

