10.4 Vital signs, physical findings, and other observations related to safety

10.4.1 Vital Signs

Vital measurements (including SBP, DBP, PR, RR and weight) are generally collected in standard units. If any measurements are collected in international units, they will be converted to standard units for summaries. Subject Listings will be prepared for vitals variables.

The observed value and change from Baseline will be summarized descriptively by treatment group and scheduled study visit. In the same table, the observed value and change from Baseline will be summarized by treatment for all scheduled visits. The Last Visit, minimum, and maximum post-baseline values during the Treatment Period will also be included.

The number and percentages of subjects with abnormal vital signs and body weight during the Treatment Period will be presented by treatment group and PSL total group. The abnormal vital sign and body weight criteria are provided in Appendix 13.2. Subject numbers for those meeting abnormal criteria will also be presented.

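### As printed, the adult vital-sign criteria in SAP 14.2 are low-only, so the count of subjects with abnormal vital signs leaves out every upward abnormality in pulse, blood pressure and respiratory rate.

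*SAP*

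**What the plan says.** SAP 10.4.1 states: "The number and percentages of subjects with abnormal vital signs and body weight during the Treatment Period will be presented", by treatment group and for the PSL groups combined. It sends the reader to Appendix 13.2 for the criteria; the table stands at 14.2.

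The population is adult (Protocol 6.1: "Subject is an adult (18 years of age or more"), so the oldest age band applies to each parameter:

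- Systolic pressure (17 years and over): "<90 and a decrease from Baseline of ≥20".
- Pulse and diastolic pressure (17 years and over), same wording in both rows: "<50 and a decrease from Baseline of ≥15".
- Respiratory rate (12 years and over): below 10 breaths per minute, with no change condition.
- Body weight (17 years and over): "≥ 10% change from Baseline (an increase or a decrease").

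The paediatric rows for pulse, blood pressure and respiratory rate also give lower limits only. SAP 14.4 gives ECG heart rate above 12 years two limits: below 50 and above 120.

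Protocol 4.2.2 lists changes in vital-sign parameters as a safety variable. Protocol 13.4.1 says that possibly clinically significant treatment-emergent abnormalities, including those in vital signs, will be listed and summarised. Neither section names a direction. SAP 3.9, which lists departures from the protocol-defined analyses, records no restriction of the vital-sign criteria to low values.

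**The concern.** The abnormality count is the only categorical vital-sign summary in SAP 10.4.1, and its label reads as covering abnormal values in general. With low-only limits it covers hypotension, bradycardia and slow breathing, and nothing on the other side. A reader comparing arms on that table would not learn how many subjects rose above a limit, and nothing in the label would say so.

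The plan is also uneven. A rate of 140 is abnormal when read from an ECG and not abnormal when recorded as pulse. Weight gain is counted, but a rise in blood pressure is not. The protocol names cardiovascular events as a potential risk (2.4) and vital signs as part of cardiac monitoring (2.3.1), so this count should be complete, or labelled for what it covers.

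**Working it through.** No power or sample-size figure lies behind this point, so there is no stated figure to reproduce. The check applies the printed rules.

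**Rules.** Let b be the Baseline value and p the post-Baseline value.

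- Pulse: abnormal if p < 50 and b − p ≥ 15
- SBP: abnormal if p < 90 and b − p ≥ 20
- DBP: abnormal if p < 50 and b − p ≥ 15
- Respiratory rate: abnormal if p < 10

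**Logic.** For the first three, the second condition forces p < b. A rise means p > b, so the two cannot both hold and no rise can be flagged. For respiratory rate, no value of 10 or above can be flagged, whatever the Baseline.

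**Enumeration.** The rules were applied to every integer pair with p > b over wide assumed ranges. A range of m integers gives m(m − 1)/2 such pairs.

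| Parameter | Assumed range | m | Rises tested | Rises flagged |
|---|---|---|---|---|
| Pulse | 30 to 220 | 191 | 191 × 190 / 2 = 18,145 | 0 |
| SBP | 60 to 260 | 201 | 201 × 200 / 2 = 20,100 | 0 |
| DBP | 30 to 160 | 131 | 131 × 130 / 2 = 8,515 | 0 |
| Respiratory rate | 4 to 60 | 57 | 57 × 56 / 2 = 1,596 | 15 |

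The 15 respiratory-rate pairs are those with both values from 4 to 9 (6 × 5 / 2 = 15), for example 8 to 9. They are flagged for being low, not for rising.

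**Examples.** SBP from 120 to 200: 200 is not below 90, so not abnormal. Pulse from 70 to 140: 140 is not below 50, so not abnormal under 14.2; the same rate on an ECG exceeds 120 and is abnormal under 14.4.

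**Where ECG heart rate can stand in for pulse.** After Day 1, the scheduled clinic visits of the Treatment Period are Visits 3 to 7. Vital signs are taken at all five. ECGs are taken at Visits 3, 4, 5 and 7, but not at Visit 6 (Protocol Table 5-1 and 8.2.3.2). The ECG count therefore covers four of the five visits for heart rate, and none for blood pressure or respiratory rate.

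**The case against.** **Increases are reported elsewhere.** This is largely right. SAP 10.4.1 summarises observed values and change from Baseline by visit, adds that "The Last Visit, minimum, and maximum post-baseline values during the Treatment Period will also be included", and provides subject listings. Protocol 11.7.1 says: "Any clinically significant abnormality in the view of the Investigator will be recorded as an AE". SAP 10.2 tabulates treatment-emergent adverse events by number and percentage of subjects, so a rise judged clinically significant does receive a subject count by arm. SAP 10.4.2 counts abnormal ECG heart rates. A reader might infer that increases are invisible, or that the trial would report a zero rate of hypertension. The documents support neither: no table is described as a rate of hypertension, and leaving a category out is not reporting zero. What survives is narrower. Adverse-event counts depend on investigator judgement, and the means and maxima give no number of subjects above a limit.

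**The upper limits may have been lost from the table text.** Cells can be lost when PDF tables are extracted. The pulse lower limits (100, 90, 60, 50) match the ECG heart-rate lower limits, each of which is paired with an upper limit. Against loss, all four parameters are low-only in every age band, the adult entries read as complete phrases, and two-limit cells survive in 14.1 and 14.4. Loss is possible but not shown, so the table needs checking first. The amendment log's superseded 10.4.1 text, which spoke of low or high values, is not evidence of an error.

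**Low-only may be deliberate.** Protocol 2.3.1 reports minor, transient falls in blood pressure, and temperature in 14.2 is also one-sided (high only). That explains having low limits but not omitting high ones, and neither document gives such a rationale.

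**The protocol does not ask for upper limits.** True: 4.2.2 names no direction, and the change-from-Baseline summaries meet it. Protocol 13.4.1 sets no limits either. The protocol should not be read as explicitly requiring both directions, but its promise of an abnormality summary is not confined to low values.

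**Conclusion.** The point holds for the categorical count and no further. If SAP 14.2 is as printed, the count of subjects with abnormal vital signs omits every upward abnormality in pulse, SBP, DBP and respiratory rate, in all four arms. The resulting gap is a threshold-based count by arm: absent for high blood pressure and high respiratory rate throughout, and absent for high pulse at Visit 6. At the other scheduled Treatment Period visits after Day 1, the ECG heart-rate count partly fills it.

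This rests on two conditions: the printed table is complete, and no separate rationale for low-only limits exists outside the two documents. How many subjects would be affected cannot be estimated from the documents. Efficacy analyses and the recording of adverse events are untouched.

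**What to change.** 1. Confirm table 14.2 against the original SAP. If upper limits are present there, only the cross-reference needs correcting.
2. If the table is as printed, add the sponsor's standard upper limits to the adult rows for pulse, SBP, DBP and respiratory rate. The documents give no upper limit for blood pressure or respiratory rate, so none is proposed here.
3. Reconcile the pulse limit with the heart-rate limit in 14.4. That row carries no change-from-Baseline condition, so it cannot be cited as the source of one for pulse.
4. Tabulate low and high values separately. If low-only was intended, give the reason and title the table as low values.
5. In 10.4.1, change the reference from Appendix 13.2 to 14.2.

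The cost is an appendix edit and extra rows in one table. The measurements are already collected. These are tabulation limits and change no clinical management.

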14.3 Echocardiogram Valvular Abnormality Grading Criteria

Echocardiogram Valvular Abnormality	Severity / Description	Potential Cardiovascular Signs/Symptoms	Action
Grade 0	Absent: no regurgitation, no stenosis	None reported	None
Grade 1	Mild: trace or barely detected regurgitation/stenosis	Minimal to none	None; continued observation
Grade 2	Moderate: regurgitation/stenosis with intermediate values	Symptoms ^a : Shortness of breath on exertion or at rest; palpitation; syncope; anginal or pericarditic chest pain; fatigue or weakness	For a Grade 2/moderate severity, a decision to discontinue is based on severity of clinical signs/symptoms; if accompanied with moderate to severe signs/symptoms this results in subject discontinuation.
Grade 3	Severe: regurgitation/stenosis in the extreme range, often accompanied by other symptoms (eg, pulmonary congestion)	Signs: Pulmonary arterial pressure >40mm Hg and rise of >10mmHg; pulmonary edema; peripheral edema or ascites; atrial fibrillation or malignant arrhythmia; hypotension	Discontinuation of subject. For a Grade 3 of severe, subject should be discontinued regardless of accompanying clinical symptoms.

Echocardiogram Valvular Abnormality	Severity / Description	Potential Cardiovascular Signs/Symptoms	Action
Grade increase by 2 levels	Increasing from: Grade 0 to 2 or Grade 1 to 3	Rapid onset of above signs/symptoms	
A jump of 2 grades to Grade 2/moderate accompanied with moderate to severe signs/symptoms results in subject discontinuation.
 
A jump of 2 grades to Grade 3/severe (with/without symptoms) will result in subject discontinuation.

^aNote: Based on the New York Heart Association Classification of symptoms. Other echocardiogram measurements are described in the study Echocardiogram Manual.

This document cannot be used to support any marketing authorization application and any extensions or variations thereof.

14.4 Abnormal Criteria for ECG

Abnormality criteria to be applied in the assessment of ECG parameter values are given below:

Parameter	Age	Abnormality Criteria
QT interval (ms)	1m-<12y	>500
	>12y	>500 or ≥60ms increase from Baseline
QTc(F) (ms)	<6m	>490, or >15% increase from Baseline
	6m-<3y	>440, or >15% increase from Baseline
	3y-<12y	>440, or >15% increase from Baseline
	>12y- <17y	>440, or >15% increase from Baseline
	≥17y	>500 or ≥60ms increase from Baseline
QTc(B) (ms)	<6m	>490, or >15% increase from Baseline
	6m-<3y	>450, or >15% increase from Baseline
	3m-<12y	>450, or >15% increase from Baseline
	>12y- <17y	>450, or >15% increase from Baseline
	≥17y	>500 or ≥60ms increase from Baseline
PR interval (ms)	<6m	>150, or >25% increase from Baseline
	6m-<3y	>170, or >25% increase from Baseline
	3y-<12y	>180, or >25% increase from Baseline
	>12y - <17y	>200, or >25% increase from Baseline
	≥17y	Treatment-emergent value >200, >220, >250
QRS interval (ms)	<6m	>90, or >25% increase from Baseline
	6m-<3y	>90, or >25% increase from Baseline
	3y-<12y	>100, or >25% increase from Baseline
	>12y - <17y	>110, or >25% increase from Baseline
	≥17y	Treatment-emergent value >100, >120, >140
Heart rate (bpm)	<6m	<100, >180
	6m-<3y	<90, >150
	3y-<12y	<60, >130
	>12y	<50, >120

Abbreviations: bpm = beats per minute; m = months; ms = milliseconds; QTc = corrected QT interval; y = years. A month is defined as 30 days; a year is defined as 365.25 days.

Note: Treatment-emergent is defined as meeting the criteria at any post-Baseline visit during the Treatment Period (including unscheduled visits) and not meeting the same criteria during Baseline

15 AMENDMENT(S) TO THE SAP

15.1 Amendment 1

Rationale for the amendment

The primary purpose of this amendment is to specify changes in the planned analyses due to early termination of the study and due to COVID-19 global pandemic impact.

Modifications and changes

Major specific changes

Change #1

The following has been changed:

2.2 Efficacy variables

Seizure-free status and seizure free days include all (Types I, II, and III) seizure types.

Changed to:

Seizure-free status include all (Types I, II, and III) seizure types.

Change #2

The following has been removed:

2.2.3 Other efficacy variables (This list applies for all regulatory authorities)

- Time to return to baseline 28-day observable focal-onset seizure count during the 12-week Maintenance Period

Change #3

The following has been added:

Table 2-1 Schedule of Assessments

Added Setting (Required Onsite) column to include data that may be collected through phone or video calls for visit, during the pandemic.

Change #4

The following has been added:

3.2.3 Analysis periods

Table 3-1: Start and end of EP0092 analysis periods

Only seizure data prior to and on the date of last dose of study medication will be included in the analysis.

Change #5

The following has been added:

3.5.6 Completer Set

The Completer Set is a subset of the FAS, consisting of those subjects who completed the 16-week treatment period.

Change #6

The following has been added:

3.7 Sites pooled strategy

To ensure at least 5 subjects in each region in the FAS at each treatment group, Japan will be pooled with North America to form a non-Europe region for the efficacy analyses.

Change #7

The following has been added:

3.9 Changes to protocol-defined analyses

Due to Covid-19 impact on site initiation and enrollment and due to early termination of the study, the following items in the protocol were updated in this SAP.

Section in this SAP	Description	Change from the protocol
2.2	Efficacy variables	Removed: Seizure-free days include all (Types I, II, and III) seizure types
2.2.3	Other efficacy variables	Removed: Time to return to baseline 28-day observable focal-onset seizure count during the 12 week Maintenance Period
Table 2-1:	Schedule of Assessments	Added Setting (Required Onsite) column to include data that may be collected through phone or video calls for visit, during the pandemic.

3.5.5	Per Protocol Set	
Due to early termination of the study, PPS will not be included in the study.
 
Removed:
 
The Per Protocol Set (PPS) is a subset of the FAS, consisting of those subjects who had at least 1 post-Baseline efficacy measurement and who had no major protocol deviation affecting the primary efficacy variable, as confirmed during a pre-analysis data review meeting, conducted prior to study unblinding.

3.10	COVID-19 eCRF	Added, see section 3.10 for details
4.3.1	Sequential Analyses	Removed all text associated with China region due to no patient enrollment and due to early termination of the study.
4.8	Examination of subgroups	
Removed: subgroup by region, gender, age
 
Added:
 
Levetiracetam/Brivaracetam use at study entry (Y/N) based on AED medication CRF.

6.2	Other Baseline characteristics	Removed text associated with China region.
8.1.2.2	Supportive and sensitivity analyses for the primary variable for submission to the US FDA, PMDA, and other regulatory authorities not referencing EMA	Removed text related to sensitivity analyses due to changed scope of the study.
8.1.2.4	Supportive and sensitivity analyses for the primary variable for submission to the EMA and regulatory authorities who reference EMA.	Removed text related to sensitivity analyses due to changed scope of the study.

8.1.3	Analysis of primary efficacy variable for submission to the CFDA	Removed text associated with China region.
-------	--	--

Change #7

The following has been added:

